A feasibility clinical trial conducted by our group tested the ReCognitionVR cognitive interventions on older and young healthy volunteers (Appendix A. Final Study Report). The results of this study showed that ReCognitionVR-based cognitive exercises were feasible, acceptable, and tolerable by older healthy subjects. In stage 2 of our research study, we want to evaluate the safety, feasibility, acceptability, and tolerability of VR-based cognitive exercises in 60-year-old or older patients following abdominal surgery admitted to the surgical floor at Houston Methodist Hospital (HMH). Our premise is that VR-based cognitive stimulation software will allow the controlled delivery of structured cognitive exercises focusing on orientation, attention, memory, and executive functions. The system will allow customized frequency and duration of cognitive exercises based on the users' difficulty level in a delightfully relaxed-environment with beach wave sounds.

Hypothesis:

We will test the hypothesis that the test population will find ReCognitionVR-based cognitive exercise safe, feasible, acceptable, and tolerable.

2. Purpose of the Study / Objectives

This study aims to assess the feasibility, acceptability, and safety of using ReCognitionVR-based software in older surgical patients. Results from this study will be used to inform the design of a future study in critically ill hospitalized patients at risk for delirium.

The question that drives this study is:

In surgical floor patients, what is the safety and feasibility of using the ReCognition VR-based cognitive exercise, and what is the acceptability and tolerability of the exercise?

OBJECTIVES AND ENDPOINTS

OBJECTIVES	ENDPOINTS	JUSTIFICATION FOR ENDPOINTS
Primary		
The primary objective of this study is the safety of VR-based cognitive stimulation exercises for older surgical patients.	The primary endpoint is the proportion of treatment-emergent adverse events (TEAE) in each group (experimental and control).	 To assess tolerability of ReCognitionVR-based cognitive stimulation exercises. Adverse events (e.g., cybersickness) will assess tolerability

Page 2 of 21

OBJECTIVES	ENDPOINTS	JUSTIFICATION FOR ENDPOINTS
		during engagement through exercise provided by ReCognitionVR games.
Secondary		

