We will report the demographic variables of age, sex, race, and ethnicity for each group and the clinical characteristics and will review the patient's medical records for body mass index, history of hypertension with active management, drinking status, smoking status, ASA status, preexisting medical co-morbidities. If not found in the medical record, we will obtain this information.

[figure not shown]
The results of this study will be reported using descriptive statistics. Continuous variables will be reported as means with standard deviation or medians and interquartile range contingent on the normality of the distribution. Categorical variables will be reported using Chi-square or Fisher's exact test, as appropriate.

5. Study Intervention

- 1. Older patients (≥ 60 years old) scheduled to undergo abdominal surgeries (open or laparoscopic or robotic assisted), small bowel and large bowel surgery; cholecystectomy; Whipple procedure; pancreatectomy; splenectomy at HMH will be invited to participate.
- 2. We will screen patients for inclusion and exclusion criteria and will assign a screening number.
- 3. After signing informed consent, participants will be enrolled in the study and randomized using computer-generated randomization software to traditional orientation method (control) or ReCognitionVR-based cognitive exercises (experimental).
- 4. The experimental group will watch a video on using VR technology, placement of a VR headset, and assessment of baseline cognitive function using the Mini-Cog screening tool.
- 5. All participants will have a frailty screening assessment.9

Page 7 of 21

- 6. The Mini-Cog screening tool will assess the patient's cognitive status of all participants. (Appendix D)⁸
- 7. The experimental group will receive a 3D- ReCognitionVR-based simulated cognitive exercise program targeting attention, organizing thinking, and motor activities using VR games. The participant will receive study intervention after arrival to the room from the operating room, free of residual anesthesia, by measuring the Richmond Sedation Scale (RASS)- Appendix E^{10} score of 0.

- 8. The detail of the software as follows:
 - 3-D Recognition Virtual Reality-Based Simulation Sessions Program: Software Platform:

The VR platform will consist of

Page 8 of 21

- The VR headsets manufactured by the Oculus Quest 2 glasses (Facebook Inc., USA) with stereoscopic vision and stereo sound will be used to show the virtual world to participants.

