- Pain scores (using numeric pain rating scale tool)
- Safety adverse events

Identifier (or parts of)	Recorded	Disclosed	Comment
All elements of dates (except year) for dates	Yes	No	Necessary for complete data
directly related to an individual, including			analysis
patient names, birth date, admission date,			
discharge date, and date of death; and all			
ages over 89 and elements of dates			
(including year) indicative of such age			
Phone numbers; Fax numbers	Yes	No	Necessary to complete a
			questionnaire
Medical record numbers	Yes	No	Necessary to organize data
			collection

Page 12 of 21

Identifier (or parts of)	Recorded	Disclosed	Comment
Any other unique identifying number,	Yes	No	Virtual cognitive
characteristic, or code			interventions are frequently
			delivered

9. Data and Specimen Banking

No specimens will be obtained, stored, or banked in this study.

10. Study Population

This study will be a single-center study of older patients who underwent abdominal surgeries and will be conducted at Houston Methodist Hospital. We will enroll 30 patients scheduled to undergo abdominal surgery who are ≥60 years of age. The rationale for enrolling older patients is that older surgical patients are at high risk for the development of delirium.

A total of 30 patients will be prospectively enrolled. 15 patients will receive the standard of care / re-orientation technique, and 15 patients will receive ReCognitionVR-based cognitive exercises. All participants will be given post-use surveys to assess usability and acceptability outcomes.

Inclusion Criteria:

- 1. Patients ≥ 60 are scheduled to undergo the following abdominal surgeries (open or laparoscopic or robotic assisted) small bowel and large bowel surgery; cholecystectomy; Whipple procedure; pancreatectomy; splenectomy.
- 2. RASS Score 0

Exclusion Criteria:

- 1. Subjects with baseline cognitive impairment.
- 2. Person with active psychiatric disorders and being treated with medications, especially schizophrenia.
- 3. Person who is deaf or blind.
- 4. Person with an underlying cognitive disorder or associated phobias (e.g., claustrophobia).
- 5. Person participating in other clinical trials involving drugs, biologics, devices, or behavioral interventions.
- 6. Active seizure disorders.

11. Screening and Recruitment

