All study data will be transmitted over an encrypted SSL connection that requires user authentication. This application is designed to be in full compliance with the International Conference on Harmonization and Good Clinical Practices (ICH-GCP), the FDA's Code of Federal Regulations (CFR) 21 Part 11 Electronic Record and Electronic Signatures, the FDA's "Guidance: Computerized Systems Used in Clinical Trials," and the Privacy Rule of the HIPAA.

HMRI policy on record retention will be followed, and human subject research data will be kept for a minimum of 6 years after the completion of the study. Research materials will be stored in \ on password-protected computer systems on a secure server on the Houston Methodist network.

The roles and responsibilities of the Investigators are (a) assuring that the trial is conducted according to the Protocol and Manual of Procedures (MOP); (b) identifying, recruiting, and enrolling participants; (c) obtaining informed consent from each participant and protecting their

Page 16 of 21

rights; (d) collecting and entering study data into REDCap, and following participants through study completion: (e) assuring regular IRB/REB review.

18. Informed Consent Documentation and Process

The informed consent will be obtained in written format using a consent document that is HMRI-approved. The investigators involved in the consent process will all be credentialed at HMRI to participate in research at HMH. System Policy and Procedure RE-12 will be followed. The PI and investigators will identify the surgical patient from the surgeon's clinic, pre-anesthesia clinic, and operating room procedures and surgery list. Potential participants may also consent on the same day of use of ReCognitionVR software. During the informed consent process, the investigator or designee, who has been trained on the protocol, will explain the nature and scope of the intervention, potential risks, and benefits of participation and answer questions from the potential participants. All participants must sign and date the Institutional Review Board (IRB) approved informed consent form.

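### The stated population is patients on the surgical floor after surgery, but eligibility never checks floor admission and randomisation may come before it is known

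*Combined protocol and SAP*

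**What the plan says.** **Stated population.** The introduction describes the people to be studied as "patients following abdominal surgery admitted to the surgical floor at Houston Methodist Hospital (HMH"). Section 2 puts the research question the same way: "In surgical floor patients, what is the safety and feasibility of using the ReCognition VR-based cognitive exercise". Section 2 also leaves critically ill patients to a future study.

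**Eligibility.** Section 10 has two inclusion criteria. The first begins "Patients ≥ 60 are scheduled to undergo the following abdominal surgeries" and lists operations from cholecystectomy to the Whipple procedure, by open, laparoscopic or robotic approach. The second is a RASS score of 0. None of the six exclusions concerns postoperative destination.

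**When a place is taken.** Section 18 says "The PI and investigators will identify the surgical patient from the surgeon's clinic, pre-anesthesia clinic, and operating room procedures and surgery list", so many patients will be approached before their operation. It adds that "Potential participants may also consent on the same day of use of ReCognitionVR software", which permits later consent but does not require it. Section 5 step 3 states "After signing informed consent, participants will be enrolled in the study and randomized using computer-generated randomization software". The Schedule of Activities instead places randomisation at Day 1, Time 1 (pre).

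**The session.** Section 5 step 7: "The participant will receive study intervention after arrival to the room from the operating room", with RASS 0.

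**What happens to those without a session.** The endpoint table in Section 2 sets feasibility as 20 minutes of use by 70% of enrolled participants. Section 12 withdraws participants who receive no study intervention and removes their data. No replacement rule is given.

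**The concern.** The aim and the eligibility criteria describe different groups. A patient can satisfy every written criterion and still fall outside the question, because RASS measures alertness and not location. If allocation follows consent, as step 3 says, a place can be used before anyone knows whether the patient will reach the floor.

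Two kinds of patient then matter. Some get no session, for example because the operation is cancelled. They either count against feasibility for a reason unrelated to the software or disappear from the data after randomisation. Others are treated somewhere other than the floor, and they contribute results to a question that was not asked about them. With 15 per arm, a few such patients are a visible share of the sample.

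**Working it through.** **Inputs from the documents.** 15 participants per arm (Section 4); feasibility target 70% of enrolled participants (Section 2, endpoint table); removal of untreated participants (Section 12). The sample size is descriptive, with no power calculation to reproduce; the total of 30 is 15 + 15.

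**Assumed inputs.** *k*, the number of VR-arm patients who get no session, and *p*, the true completion probability among the other 15 − *k*. The documents give neither.

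**Step 1: the target as a count.** 0.70 × 15 = 10.5, so 11 completers are needed; 10/15 = 66.7% falls short.

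**Step 2: all 15 stay in the denominator (Section 2).** The chance of meeting the target is P(X ≥ 11) with X ~ Binomial(15 − *k*, *p*).

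| *p* | *k*=0 | *k*=1 | *k*=2 | *k*=3 |
|---|---|---|---|---|
| 70% | 51.5% | 35.5% | 20.2% | 8.5% |
| 85% | 94% | 85% | 69% | 44% |
| 90% | 98.7% | 95.6% | 86.6% | 65.9% |

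At *k* = 5 only 10 patients can complete, so the target is out of reach whatever *p* is.

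**Step 3: untreated patients are removed (Section 12).** The denominator becomes 15 − *k*, and the number needed is 0.70 × (15 − *k*) rounded up: 11 of 15, 10 of 14 (from 9.8), 10 of 13 (from 9.1) and 9 of 12 (from 8.4).

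| *p* | *k*=0 | *k*=1 | *k*=2 | *k*=3 |
|---|---|---|---|---|
| 70% | 51.5% | 58.4% | 42.1% | 49.3% |
| 85% | 93.8% | 95.3% | 88.2% | 90.8% |

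The steep fall in step 2 is gone. The movement that remains comes from rounding the target to whole patients.

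**Step 4: what removal costs.** Precision for the primary safety endpoint drops. With zero adverse events in *n* patients, the exact two-sided 95% upper limit is 1 − 0.025^(1/*n*): 21.8% for *n* = 15 and 26.5% for *n* = 12. The feasibility denominator is then also no longer the enrolled participants.

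**Step 5: the two timings.** If randomisation follows step 3 for a patient consented in clinic, *k* can exceed 0. If it follows the Schedule, on Day 1 just before the session, cancelled operations and patients never ready for a session should already have dropped out, and *k* may be close to 0. Even then no written criterion stops a patient in a non-floor bed from being randomised.

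**The case against.** The strongest reply is that the practical effect may be small. The Schedule's timing, step 7's requirement for arrival in a room at RASS 0, and the option of same-day consent could together mean that almost nobody is allocated before the destination is known. Section 12 removes untreated patients, which takes away most of the effect on feasibility. Feasibility is a secondary endpoint, the analysis is descriptive, and delirium is exploratory. The specific neurological, cardiac and pulmonary events in Section 14 are mostly tied to the first 5 minutes of the session. All healthy volunteers in the preliminary study completed the exercise (Section 3), so 70% is a harsh scenario: at 95% completion with all 15 retained, the chance is still 99.6%, 97.5% and 88.2% for *k* = 1, 2 and 3.

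Much of this stands as a limit on size. It does not remove the mismatch: step 3 is current text and contradicts the Schedule, Section 12 contradicts the enrolled-participants denominator, and none of the safeguards tests floor admission.

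A reader might go further and infer that patients who do not reach the floor cannot have the session. The documents do not support that. Step 7 refers to a room, not a floor bed. A critical-care patient at RASS 0 could have the session and later delirium checks, and a same-day patient could complete 20 minutes before leaving. Only a cancelled operation clearly rules the session out. Nor do the documents support treating the fall to 8.5% as the expected effect: it needs three lost patients, 70% completion and no removal under Section 12.

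**Conclusion.** The mismatch is established by the text: the population is stated as surgical-floor patients, eligibility does not require floor admission, and the two statements of randomisation timing disagree. As written, places can go to patients outside the trial's own question.

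The size is conditional. With everyone retained and 85% completion, one to three VR-arm patients without a session lower the chance of meeting the target from 94% to between 85% and 44%. With removal it stays at 88–95%, at the price of post-randomisation exclusions and a wider safety interval. Both branches rest on an assumed *k*; if the Schedule's timing is the one followed, *k* may be near 0. The point merits an amendment because the change is cheap and specific, not because the documents show that the loss will be frequent.

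It would be wrong to conclude that a floor-admission criterion secures the 24–72 hour data. A floor patient discharged early would satisfy it and still miss later visits.

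**What to change.** 1. In Section 10, add surgical-floor admission after the operation as an eligibility check, confirmed in both arms before randomisation.
2. Reconcile Section 5 step 3 with the Schedule of Activities so that randomisation follows that check. Consent may still be taken earlier.
3. Log consented patients who are not admitted to the floor as screen failures, with the reason, so that the report can show how many there were.
4. Separately, reconcile the 24, 48 and 72 hour visits with the Section 5 statement, in the text on the control method, that participation ends at discharge. Items 1–3 do not resolve this.

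The cost is a short amendment touching Section 10, step 3 and, if needed, the Schedule. The total stays at 30. Some consented patients become screen failures, so a few more must be approached. No rule on where patients should be placed after surgery is implied.

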Only the minimum amount of personal information needed to conduct this study will be collected regarding participants' privacy interests. Study participants will be informed that the only individuals who can see un-coded personal health information include the following: the Study Doctor, other employees who work on this study (including the Institutional Review Board) at the hospital, employees of the sponsor who check that this study is being done correctly, and

Page 14 of 21

regulatory authorities where required by law. In addition, participants will be carefully informed about the Release of Health Information section in the Informed Consent Form (ICF), which describes who will access their information and how it will be used. We will emphasize that participation in this study is voluntary and that participants can choose at any time to cease participation and revoke authorization to use and disclose their information.

14. Risks to Subjects

The risks below are associated with the use of the Oculus Quest 2 VR Headset Device.

All adverse events (AEs) will be captured and recorded at each time point. We will report AEs as a proportion of study participants who developed AEs.

Specific AEs to be monitored will include:

Neurological AEs: (Cybersickness is defined as new-onset blurry vision, double vision, dizziness, headaches, eye fatigue, drowsiness, disorientation, and apathy) within 5 minutes after starting the study intervention).

Cardiac Adverse Events: New-onset hypotension (SBP <90 mmHg and DBP <60 mmHg), Bradycardia (HR < 50), Tachycardia (HR> 100), and Arrhythmias (Supraventricular or ventricular) with HR> 150 beats per minutes within 5 minutes after the starting of 3D Simulated VR sessions. Or changes >20% from baselines.

Pulmonary Adverse Events: New-onset hypoxia: SpO2 < 88%, Respirator rate > 35 breaths/minute within 5 minutes after starting 3D Simulated VR sessions.

The safety precautions to minimize the risk to participants are as follows:

- *Vital signs BP*, HR, RR, SPO2, and pain scores (using numeric pain rating scale tool) will be monitored before, during, and after using ReCognitionVR software.

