- Mitigation strategy: The gaming environment underwent careful consideration to alleviate cybersickness. We have limited neck motion in the games to avoid sensory conflict, as the subject will remain seated or in a bed during use. Both controllers can still move freely, and the game's design was such that the game could be played from a seated position. In addition, study observers can quickly intervene if a subject begins to feel cybersickness symptoms. The study subjects will be recommended to close eyes and take off the headset until the symptoms subside.

Other Risks

You may be at risk for loss of confidentiality, meaning your information could become known to someone not involved in this study. If this happens, it could result in damage to your reputation, which could also affect your relationships with family and friends, affect your employment, or make it harder to get insurance or a job.

Page 15 of 21

15. Potential Benefits

Direct benefit to participants is not anticipated. The data from this study is expected to inform a subsequent clinical trial of using the ReCognition VR-based software in patients at risk for delirium.

16. Financial and Economic Issues

The participants in this study will not be compensated, and there is no additional cost to participants for taking part in this study.

17. Data Safety Plan

- The research team plans to periodically evaluate data collected regarding the benefits and harms of the study to evaluate the participants' safety.
- Data reviewed periodically will be the following:
 - Adverse effects occurred during the study intervention (dizziness, double vision, disorientation, etc.)
 - Adverse effects during and after the study intervention
 - o Delirium on days 1, 2 and 3
- Safety information will be collected during study visits.
- Data collection will occur during the game. Specifically, after the user plays the minigame in the ReCognitionVR Software. Safety data collection will begin before the study intervention and also be collected during and after the study intervention.

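### The 5-minute onset limit in Section 14 conflicts with that section's all-AE rule and the vital-sign schedule, and the undefined primary TEAE proportion is tied to neither

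*Combined protocol and SAP*

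**What the plan says.** **Primary endpoint.** Section 2 (objectives and endpoints table) sets a TEAE proportion for the experimental and control arms as primary, and its justification gives cybersickness as the example event. TEAE has no definition, onset period or counting rule, and the data analysis plan in Section 4 does not mention it. Under its primary objective Section 4 lists something else: mean changes in SpO2, respiratory rate and blood pressure, which Section 2 calls secondary.

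**General AE rule, Section 14.** Capture is unrestricted: "All adverse events (AEs) will be captured and recorded at each time point". The unit of reporting is then set as the participant: "We will report AEs as a proportion of study participants who developed AEs".

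**Specific AEs, Section 14.** The cybersickness definition ends "eye fatigue, drowsiness, disorientation, and apathy) within 5 minutes after starting the study intervention". The cardiac entry includes "Bradycardia (HR < 50), Tachycardia (HR> 100" and ends "within 5 minutes after the starting of 3D Simulated VR sessions. Or changes >20% from baselines". The pulmonary entry reads "New-onset hypoxia: SpO2 < 88%, Respirator rate > 35 breaths/minute within 5 minutes after starting 3D Simulated VR sessions". Blood pressure, heart rate, respiratory rate, SpO2 and pain "will be monitored before, during, and after using ReCognitionVR software"; no times are given.

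**Timing elsewhere.** Section 5 (Dosing) gives a session of about 20 minutes. The Schedule of Activities places SpO2, respiratory rate and blood pressure at pre, 10 minutes and post, has no heart-rate row, and runs AE review from pre to 72 hours. Section 17 lists "Adverse effects occurred during the study intervention (dizziness, double vision, disorientation, etc" with no 5-minute limit, and a further item covers effects during and after the intervention.

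**Controls.** Section 5 has their oxygen level, breathing and blood pressure taken at unspecified standard-care times. Their participation ends at discharge.

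**The concern.** Section 14 holds two rules that could decide who counts in the primary proportion. One takes any AE at any time point, per participant. The other recognises certain events only if they begin in the first 5 minutes. Nothing says which one TEAE follows. Staff working from different sentences of the same section could label or count the same participant differently.

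The windowed rule also fits poorly with the rest of the plan. It ends before the first scheduled reading after the start, and it has no meaning in the control arm, although the endpoint is reported for both arms. The results are meant to inform a later trial in patients at risk for delirium, so an unclear safety proportion would carry forward.

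**Working it through.** **1. Inputs.** Window: 5 minutes (Section 14). Session: about 20 minutes (Section 5, Dosing). Scheduled readings after the start: 10 minutes and post (Schedule). Arm size: 15, and 15 + 15 = 30 as stated (Section 4). The plan gives no target rate, margin or precision for the AE proportion, so it has no figure of its own to reproduce.

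**2. What the 5-minute phrase limits.** In the cardiac and pulmonary entries the phrase follows the last item in the list, so it may limit the whole list or only that item.

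| Criterion | Phrase limits whole entry | Phrase limits last item only |
|---|---|---|
| Cybersickness symptoms | 5 min | 5 min |
| Hypotension, HR < 50, HR > 100 | 5 min | no window stated |
| Arrhythmia with HR > 150 | 5 min | 5 min |
| Change > 20% from baseline (cardiac entry) | no window stated | no window stated |
| SpO2 < 88% | 5 min | no window stated |
| Respiratory rate > 35 | 5 min | 5 min |

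**3. Window against session and schedule.** Share of session covered: 5/20 = 25%, leaving 15/20 = 75% outside. Readings after the start that fall within 5 minutes: 0 of 2 (10 minutes; post, about 20 minutes). In a session of planned length, the whole-entry reading therefore lets no scheduled value meet the SpO2 or respiratory-rate criterion. The 20% limb does not help, because it sits in the cardiac entry. Only the unscheduled monitoring during use could supply a qualifying value.

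**4. Two example events under each rule.**
- Dizziness beginning at minute 8. Under the all-AE rule it is an AE and loses only the cybersickness label. Under the windowed rule it may not count. Section 17 treats dizziness during the intervention as an adverse effect without a time limit.
- SpO2 of 87% at the 10-minute reading. A patient may report a symptom unprompted, but it takes a criterion to turn a reading into an AE. If the window governs SpO2, no listed criterion does so here.

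**5. Control arm.** The window runs from the start of a VR session, and controls have none. The all-AE rule can be applied in both arms. AE review is scheduled to 72 hours, control participation ends at discharge, and no rule covers discharge before 72 hours.

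**6. Size.** One participant reclassified: 1/15 = 6.67 percentage points. As an illustration (the plan specifies no intervals), the exact 95% upper limit for 0/15 is 1 − 0.025^(1/15) = 21.80%. The exact interval for 1/15 is 0.17% to 31.95%. A single reclassification from 0 to 1 thus raises the upper limit by 31.95 − 21.80 = 10.15 points.

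**The case against.** The strongest reply is that the plan already leans towards the all-AE rule. Section 14 states that rule first and then gives an inclusive list of specific events. It opens by tying the risks to the headset, so the list looks device-specific. That the window cannot be applied to controls suggests it was never the counting rule for a two-arm endpoint. AE review to 72 hours and Section 17 point the same way. This stands: later symptoms would probably be recorded. It does not settle the threshold-based vital-sign events, where the listed criterion decides whether a reading is an AE at all, and it leaves TEAE undefined.

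Two further replies carry some weight. Section 14 promises monitoring during use, and the 20% limb has no window, so some cardiac changes count on any reading. A short window might also help separate VR effects from ordinary postoperative symptoms. The documents do not give that purpose, and recorded onset times would serve it without narrowing the definitions.

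A reader might infer that three quarters of events would be lost, or that the primary proportion counts only the first 5 minutes. The documents support neither. The 25% is a share of time, not of events; no onset times are given; and no sentence restricts the primary proportion to windowed events. Nor should weight be placed on heart rate being absent from the Section 8 data list, since that list, as it reads here, also lacks blood pressure, which is scheduled. The missing Schedule row is the sound evidence.

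**Conclusion.** The inconsistency is real and should be settled before data collection. Section 14 limits cybersickness to the first 5 minutes and, on one reading, the absolute cardiac and pulmonary criteria too. This conflicts with its own all-AE rule, the 72-hour AE review and Section 17, and has no anchor in controls. The likely effect is on event labels and on vital-sign AEs defined by thresholds, at 6.67 points of an arm's proportion per reclassified participant. The number affected cannot be estimated.

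The conclusion rests on a session of about 20 minutes, 15 analysed per arm, and the readings being taken as scheduled. The wider effect on cardiac and SpO2 criteria depends on the whole-entry reading. The study is descriptive and has no safety decision rule, so this does not invalidate the design.

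**What to change.** 1. State that the primary TEAE proportion follows Section 14's existing all-AE, per-participant rule. Reconcile this with Section 4, which lists vital-sign mean changes under the primary objective.
2. Remove the 5-minute limit from the AE definitions, leave every threshold unchanged, and apply the listed criteria over the whole session through the post reading.
3. Record onset time. Report in-session events separately from later events up to 72 hours or discharge, using one reference start time that works in both arms.
4. Add heart rate to the Schedule at the VR session time points, because Section 14 already monitors it and uses it to define AEs. Use control heart-rate values only where standard care records them.

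The cost is protocol wording plus onset-time and heart-rate fields on the case report form. The reported proportion may be higher than under the windowed reading and may include ordinary postoperative symptoms. Control readings will not match VR readings in timing. Both should be stated as limitations.
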